- **Highly Probable:** The event followed a reasonable temporal sequence from the time of investigational drug administration; and followed a known response pattern to the investigational drug; and could not be reasonably explained by other factors, such as the subject’s clinical state, therapeutic interventions, or concomitant medications administered to the subject; and either occurred immediately following investigational drug administration or improved on stopping the investigational drug or reappeared on repeat exposure.

Duration

The duration of the AE should be recorded using the following criteria:

- **Start:** Date of the first episode of the AE or date of significant sustained worsening in severity
- **Stop:** Date when AE either ceased permanently or changed in severity

Frequency

The duration of the AE should be recorded using the following criteria:

- **Single:** Experienced once, without recurrence
- **Recurrent:** More than one discrete episode with the same severity

Action Taken with Investigational Drug

- **None:** No change in study drug
- **Interrupted:** Investigational drug temporarily stopped
- **Discontinued:** Investigational drug discontinued permanently

Therapy

- **None:** No new treatment instituted
- **Medication:** New treatment initiated as a direct result of AE
- **Other:** Other action required

Outcome

- **Ongoing:** AE has not yet stopped
- **Resolved, no sequelae:** Subject has fully recovered
- **Resolved, with sequelae:** The AE has stopped, but the subject has a residual effect directly related to the AE
- **Death:** The subject died as a result of the AE
- **At Death, ongoing:** AE ongoing at time of subject death

Seriousness

- **Not serious:** Does not meet the criteria described in Section 6.2.7.2
- **Serious:** Meets the criteria described in Section 6.2.7.2

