## **5.5 Subject Enrollment and Disposition**

Subject enrollment by protocol amendments and subject counts by study center and prior study will be summarized.

A summary of subject disposition will display the number of subjects enrolled, received study drug, and remained in the study (using visit dates recorded on the vital signs CRF) at the beginning of the following time periods: first 4 weeks (Study Days 1 to 28), 1 to 3 months (Study Days 29 to 91), >3 to 6 months (Study Days 92 to 183), >6 month to 1 year (Study Days 184 to 365), >1 to 2 years (Study Days 366 to 730), >2 to 3 years (Study Days 731 to 1095), >3 to 4 years (Study Days 1096 to 1461) and >4 years (Study Days >=1462). Also included in this summary will be subject discontinuations showing the number of subjects who terminated from the study according to the reason for study termination/discontinuation (Investigator reported and Sponsor re-classified). Reasons for study termination will also be summarized by the time period specified above.

The withdrawal reasons as reported by the investigators on the eCRF are:

- Adverse event
- Death
- Disease progression
- Subject's voluntary withdrawal of consent (Voluntary withdrawal of consent)
- The Investigator determines that continuation in the study would be detrimental to a subject's well-being because of development of a serious illness, any other significant change in clinical status, or any other compelling medical reason (Investigator decision)
- Subject fails to comply with protocol requirements (Subject non-compliance)
- Lost to follow-up
- At discretion of Sponsor (Sponsor decision)

To better understand the discontinuation pattern, ACADIA reviewed the withdrawal reasons and in some cases, on the basis of verbatim comments in the eCRF, re-classified the reasons for discontinuation using the following categories:

- Adverse event
- Death
- Lack of efficacy / PDP progression
- PD /Concomitant disease progression
- Voluntary withdrawal of consent
- PDP improvement
- Investigator decision
- Subject non-compliance
- Lost to follow-up
- Sponsor decision

Subject disposition and study completion by Investigator-specified and Sponsor-reclassified reasons for termination will be presented in data listings and summary tables. Dispositions will also be summarized by 3 regions: North America (US and Canada), Europe and India.

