## 5.7 Study Drug Exposure and Overall Compliance

### 5.7.1 Study Drug Exposure

For the final CSR, all subjects' study drug (pimavanserin) exposure will be calculated as last dose date minus first dose date + 1. For the interim report(s), the drug exposure will be censored at the database snapshot date for the on-going subjects. For example, if a subject had withdrawn from the study before the database snapshot, then the exposure duration for this subject is last dose date minus first dose date + 1; if a subject was still ongoing at the database snapshot date, then the exposure duration for this subject is database snapshot date minus first dose date + 1.

A summary of study drug exposure will include the duration of exposure as a continuous measure in days and a categorical measure for the intervals (1-28 days, 29-91 days, 92-183 days, 184-365 days, 366-730 days, 731-1095 days, 1096-1461 days,  $\geq 1462$  days). Total amount of administered pimavanserin (mg) will be estimated by (duration of exposure\*40 mg). Study drug exposure by Sponsor re-classified termination reasons will also be summarized. Study drug exposure for subjects who died will also be summarized.

Study drug exposure measures as described above will be presented in a listing.

Since this is an open-ending study, time on pimavanserin treatment (time on study) will be evaluated for all subjects and by subgroups: baseline age group ( $\leq 75$  years old or  $> 75$  years old), gender (female or male), and geographic area (North America or outside North America). For subjects who have discontinued from study, the days on pimavanserin treatment in study -015 (not counting the exposure duration from the preceding study) will be calculated as last dose date minus first dose date + 1; otherwise the time on study will be censored at database snapshot date and will be calculated as database snapshot date minus first dose date + 1. Kaplan-Meier estimates of percent subjects on treatment at 6 months (183 days), 1 year (365 days), 1.5 years (548 days), 2 years (730 days), 2.5 years (913 days), 3 years (1095 days), 3.5 years (1278 days) and 4 years (1461 days), as well as median days on treatment will be presented.

In addition, Kaplan-Meier estimates percent subjects free of AEs leading to study termination or drug withdrawal and median days to due to AEs leading to study termination or drug withdrawal will be summarized for all subjects and by

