aforementioned subgroups. For this analysis, if a subject has an AE leading to study termination or drug withdrawal, the time to event will be calculated as last dose date minus first dose date + 1; otherwise the time to event will be censored at either last dose date (for subjects who discontinued due to reasons other than AE) or database snapshot date (for ongoing subjects).

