### **5.13.2 Deaths and Other Serious and Significant Adverse Events**

Treatment-emergent SAEs, TEAEs leading to discontinuation from the study or study drug, and TEAEs with fatal outcome will be summarized by time period as given in [Table 2](#) in frequency tables by SOC and preferred term. In addition, the overall AE summary table will also be presented for all events (i.e. treatment-emergent plus non-treatment-emergent events).

Subject listings of SAEs, deaths, and AEs leading to discontinuation of study drug will be provided. These listings will provide all relevant eCRF data for each event including the date/study day of onset, date/study day resolved, date of last dose/study day of last dose, severity, outcome, relationship to study drug, action taken, and seriousness.

Kaplan-Meier estimates of percent surviving subjects at 6 months, 1 year, 1.5 years, 2 years, 2.5 years, 3 years, 3.5 years and 4 years, as well as median survival time will be computed for all subjects and by subgroups: baseline age group ( $\leq 75$  years old or  $>75$  years old), gender (female or male), and geographic area (North America or outside North America). If a subject is deceased, the survival time will be calculated as death date minus first dose date + 1; otherwise the survival time will be censored at the last dose date (for subjects who have discontinued from the study) or database snapshot date (for ongoing subjects).

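### Kaplan-Meier estimates of AE-related discontinuation censor competing exits, so they overstate the proportion of subjects who stop for an AE, by more as follow-up lengthens

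*SAP*

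**What the plan says.** SAP 5.7.1 first plans a Kaplan-Meier analysis of time on treatment, then adds a second one: "Kaplan-Meier estimates percent subjects free of AEs leading to study termination or drug withdrawal", with a median, for all subjects and by age group, gender and geographic area.

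The rule for the second analysis has two steps. The event test comes first: "if a subject has an AE leading to study termination or drug withdrawal, the time to event will be calculated as last dose date". Days are counted from the first dose, with that day included. For everyone else, "otherwise the time to event will be censored at either last dose date (for subjects who discontinued due to reasons other than AE"). Ongoing subjects are censored at the database snapshot.

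SAP 5.5 supplies the reasons for leaving. The list opened by "The withdrawal reasons as reported by the investigators on the eCRF are" has adverse event as one entry. Death, disease progression, withdrawal of consent, investigator decision, non-compliance, loss to follow-up and sponsor decision are separate entries.

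No cumulative incidence estimate is planned for this endpoint. Related descriptive output is planned. SAP 5.5 says "Reasons for study termination will also be summarized by the time period specified above", and SAP 5.13.2 says "TEAEs leading to discontinuation from the study or study drug, and TEAEs with fatal outcome will be summarized by time period".

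**The concern.** The Kaplan-Meier estimator treats a censored subject as still able to have the event later, at the same risk as those who remain. That suits an ongoing subject censored at the snapshot. It does not suit a subject whose study treatment has ended for another clinical reason, because that subject can never discontinue study drug for an AE.

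The curve therefore answers a hypothetical question: how many would stop for an AE if nobody left for any other reason. The SAP's label, a percentage of subjects, will be read as the proportion in this trial. The two differ whenever other exits occur, and many are likely here. Protocol 1 says psychosis raises mortality in this population, Protocol 1.3 calls the population older and fragile, and Protocol 3.3 leaves treatment open-ended.

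Tolerability is part of the primary objective. If other exits differ by age, gender or region, the gap will also differ between the planned subgroups, and a subgroup contrast could partly reflect that.

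**Working it through.** **Inputs.** The documents give no discontinuation rate, event count or sample size calculation for this analysis (SAP 2.4 states not applicable), so there is no figure of the plan to reproduce. All hazards below are assumptions, taken as constant:
- a = hazard of AE discontinuation, 0.10 to 0.30 per year
- o = hazard of all other exits, 0.10 to 0.60 per year

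The horizon of 4 years (1461 days) is the one stated for the time-on-treatment curve ("3.5 years (1278 days) and 4 years (1461 days), as well as median days on treatment will be presented"). SAP 5.7.1 does not restate time points for the AE curve.

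**Formulas.**
- Percent free by Kaplan-Meier: exp(−a·t)
- Actual cumulative incidence (CIF): a/(a+o) × [1 − exp(−(a+o)·t)]
- Proportion not discontinued for an AE: 1 − CIF

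**One case in full**, a = 0.20, o = 0.40, t = 1461/365.25 = 4 years:
- Kaplan-Meier: exp(−0.80) = 44.9% free
- CIF: 0.20/0.60 × [1 − exp(−2.40)] = 0.333 × 0.909 = 30.3%, so 69.7% free
- Gap: 69.7 − 44.9 = 24.8 points

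**Range** (percent free, Kaplan-Meier vs 1 − CIF; gaps taken before rounding):

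| a, o per year | 1 year | 2 years | 4 years |
|---|---|---|---|
| 0.10, 0.10 | 90.5 vs 90.9 (0.5) | 81.9 vs 83.5 (1.6) | 67.0 vs 72.5 (5.4) |
| 0.20, 0.40 | 81.9 vs 85.0 (3.1) | 67.1 vs 76.7 (9.7) | 44.9 vs 69.7 (24.8) |
| 0.30, 0.60 | 74.1 vs 80.2 (6.1) | 54.9 vs 72.2 (17.3) | 30.1 vs 67.6 (37.5) |

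The first and last rows are the smallest and largest gaps over the assumed range. With o = 0 the two quantities are identical.

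**Simulation check** of the middle row (400 subjects, 500 runs, administrative censoring uniform between 0.5 and 6 years): 67.2% vs 76.8% at 2 years and 44.7% vs 69.7% at 4 years, in agreement with the formulas.

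**Median.** With a = 0.20, Kaplan-Meier gives ln 2/0.20 × 365.25 = 1266 days. With o = 0.40, at most 0.20/0.60 = 33% of subjects would ever stop for an AE, so half of them never reach the event and the actual cumulative incidence has no median.

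**Direction.** It does not depend on constant hazards. The cumulative incidence weights the AE hazard at each time by the probability of still being on treatment. Kaplan-Meier weights the same hazard by a probability that ignores other exits, which is never smaller.

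**The case against.** Several points on the other side stand.

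- **Deaths.** A reader might infer that the SAP censors every death and counts every fatal AE as AE-free. The text does not establish that. The event test comes first and asks whether the subject has an AE that led to termination or withdrawal, not which disposition reason was ticked. In Protocol 6.2.7.1 an AE record carries both an action taken with the drug and an outcome, including "The subject died as a result of the AE". A fatal AE flagged as ending treatment may already be an event. What the SAP lacks is a rule that says so.
- **Meaning.** The curve is not meaningless. It summarises the cause-specific hazard of AE discontinuation, and under independent censoring it can be read as a net probability. It is a different quantity from the one its label suggests.
- **Importance.** SAP 5.7.1 introduces this as an additional analysis. Time on treatment, where every discontinuation counts, and survival (SAP 5.13.2) have their own Kaplan-Meier analyses. SAP 5.1 plans no formal tests.
- **Other output.** Counts by reason and period let a reader set the curve beside what happened. This offsets the problem only in part: they do not give a cumulative proportion at fixed times that allows for unequal follow-up of ongoing subjects, and they do not correct the curve or its median.
- **Size.** The gaps rest wholly on assumed hazards and are modest at 1 year.

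**Conclusion.** The point holds as a matter of estimand and labelling. With non-AE exits censored, one minus Kaplan-Meier exceeds the actual cumulative proportion discontinuing for an AE, and the gap grows with follow-up: about 0.5 to 6 points at 1 year and 5 to 38 at 4 years, if AE hazards are 0.10 to 0.30 per year and other exits 0.10 to 0.60. The direction is certain once competing exits occur; the size is illustrative.

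A reader might suppose that the method flatters the drug. The competing-risk effect does the opposite, because it overstates AE discontinuation. If subjects who left for other recorded reasons had a higher underlying AE risk, the net reading could be too favourable, but the documents cannot show whether or how far. No test or decision rule is affected. This is a cheap improvement to a descriptive analysis.

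**What to change.** 1. Report the Aalen-Johansen cumulative incidence of AE-related discontinuation, overall and for the planned age, gender and geographic subgroups. Treat deaths without a qualifying AE and other clinical or subject-level withdrawals as competing events.
2. Keep ongoing subjects and purely administrative exits censored, for example sponsor closure or commercial availability. The SAP 5.5 list has no completion category, so such exits may be recorded under sponsor decision and must be separated. Treated as competing events, they would lower the reported incidence mechanically.
3. Keep the Kaplan-Meier estimates as a secondary display, labelled as a net, cause-specific summary.
4. State that a fatal TEAE that ended treatment counts as an AE-discontinuation event whatever withdrawal reason was ticked. Do not count all deaths as events: that would change the endpoint to a composite and overlap the survival analysis in SAP 5.13.2.

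The cost is SAP wording and a small amount of extra programming, with no new data. The downside is that the new figures will not be directly comparable with any Kaplan-Meier outputs already produced.

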## **5.8 Important Protocol Deviations**

Protocol deviation logs will be reviewed and the deviations will be categorized by deviation type and grouped as major or minor.

A summary of the number and percentage of subjects with major deviations by deviation category will be provided. A listing of major protocol deviations by site and subject will also be provided.

## **5.9 Analysis of Demographic and Baseline Characteristics**

### **5.9.1 Demographics and Baseline Characteristics**

Demographic data (age at 015 first dose date, sex, and race) will be summarized for all subjects for the safety analysis set using descriptive statistics. Summary of age categories (<65, 65-75, and >75 years) will also be presented. Race/ethnicity will be presented as White, Black, Asian and other. Region will be presented as North America (US and Canada), Europe, and India. In addition, subject counts from 2 geographic areas, North America and outside North America (Europe and India combined) will also be presented since the number of subjects (N=18) in India was too small to make meaningful comparisons. The geographic areas will be used for summarizing the clinical rating scales ([Section 5.11](#)) or mortality ([Section 5.13.2](#)).

Demographic information as described above, along with childbearing status, method of birth control for subjects of childbearing potential, and date of birth will also be presented in a data listing.

Baseline characteristics will include weight (kg), height (cm), BMI (kg/m^2), and questionnaire scores for SAPS-PD, SAPS-H+D, SAPS-H, SAPS-D, UPDRS II+III, UPDRS II, and UPDRS III. These parameters will be summarized with descriptive statistics. For the questionnaire scores the last value from the core study will serve as the baseline value of the current study. Each of these parameters will also be presented in a data listing.

### **5.9.2 Prior, Post and Concomitant Medications**

Medications started prior to the day of the first dose of open-label study medication and continued into the study, or medications started on or after the day of the first dose of study medication and before or on the day of the last dose of the study medication will be reported as concomitant medications. Medications stopped before the first date of study medication dosing will be considered prior medications. Medications started after

the day of last dose of study medication will be considered post-treatment. Prior, concomitant and post-treatment medications will be listed.

The number and percentage of subjects using concomitant medications in each WHO Drug Anatomical/Therapeutic/Chemical (ATC) Level 3 (i.e., pharmacological subgroup) category and preferred term will be summarized. Separate summaries will be presented for

- Anti-psychotic medications
- Medications indicated for dementia
- Medications indicated for motor function
- Medications not included in the preceding 3 categories.

Number of concomitant medications will be summarized at first dose date and last dose date for overall, indicated for motor functions, dementia and antipsychotics.

Antipsychotics taken post-treatment (medication started after the last dose date) will also be summarized. Multiple medications for the same subject may be classified to the same ATC level or preferred name. However, subjects will only be counted once for each level of classification.

Prior, concomitant, and post-treatment medications with the verbatim, ATC level 3 category, preferred term, indication, dosage, route, unit, frequency, and start/stop dates of administration will be provided in a listing.

### **5.9.3 Medical History**

A listing of the body system, verbatim condition/abnormality/procedure, date of onset, and an indicator for whether or not the condition is still present at baseline will be provided. A summary table will also be provided.

### **5.10 Analysis of Pharmacokinetic Data**

For the final clinical study report, pimavanserin plasma concentration data will be listed by subject with derived visit, most recent pimavanserin dose date and time, and PK sample collection date and time. No summary table will be generated.

### **5.11 Analysis of Clinical Rating Scales**

#### **5.11.1 Scale for the Assessment of Positive Symptoms**

The Scale for the Assessment of Positive Symptoms (SAPS) was designed to measure positive psychotic symptoms. Positive symptoms include delusions, hallucinations, abnormalities in language and behavior, and disordered thought processes. Two of the SAPS subscales, Hallucinations and Delusions, will be administered in this trial as a 20-item assessment. The SAPS Hallucinations scale contains 7 items and the Delusions scale contains 13 items. The score for each item ranges from 0 to 5 (0 = absent, 1 =

questionable, 2 = mild, 3 = moderate, 4 = marked, 5 = severe). The last item of each scale is the “Global rating of severity” for the corresponding domain. The combined score for SAPS-H+D will be derived as the sum of the 20 items, including the global ratings. Possible scores range from 0 to 100. If one or more of the 20 items is missing, the combined score is considered as missing at the visit. The SAPS questionnaire will be administered at the Month 1 (Week 4) visit only. Note that the baseline SAPS scores were measured at the end of preceding study.

Nine of these 20 items from the SAPS Hallucinations and Delusions domains were found to be more prevalent in PDP subjects with more severe symptoms and therefore these items are expected to have improved clinical relevance and face validity. This PD-adapted version of the SAPS (SAPS-PD; Voss et al., 2013) includes these 9 items:

- H1 Auditory Hallucinations;
- H3 Voices Conversing;
- H4 Somatic or Tactile Hallucinations;
- H6 Visual Hallucinations;
- H7 Global Rating of Severity of Hallucinations;
- D1 Persecutory Delusions;
- D2 Delusions of Jealousy;
- D7 Ideas and Delusions of Reference;
- D13 Global Rating of Severity of Delusions.

The SAPS-PD (9-item sum score), SAPS-H+D (20-item sum score), SAPS-H (hallucination subscale sum score), and SAPS-D (delusion subscale sum score) data will be summarized for all subjects and by geographic area (North America or outside North America) and by prior treatment (placebo, pimavanserin 10 mg, pimavanserin 20 mg, or pimavanserin 40 mg). Within North America, the SAPS-PD data will also be summarized by prior treatment.

The GSAPS-H+D (sum score of global rating of hallucination severity and global rating of delusion severity), GSAPS-H (global rating of hallucination severity), and GSAPS-D (global rating of delusion severity) data will be summarized for overall subjects.

The SAPS-PD, SAPS-H+D, SAPS-H, SAPS-D, GSAPS-H+D, GSAPS-H, GSAPS-D, and SAPS individual item scores will be presented in listings.

### **5.11.2 Caregiver Burden Scale**

The Caregiver Burden Scale (CBS) is a 22-item questionnaire completed by the subject’s caregiver. Each item is rated on a scale of 0 - 4 where 0 = never, 1 = rarely, 2 = sometimes, 3 = frequently, 4 = nearly always. The total score of the Caregiver Burden Scale will be derived as the sum of the 22 items, with a possible range of 0 to 88. The total score and change from baseline will be summarized by visit. The data will also be summarized within each geographic area (North America and outside North America).

